7.2. Sensitivity analysis of primary outcome

The following sensitivity analyses will be performed on the primary outcome:

- Inclusion of symptomatic residents without a positive test in the "SARS-CoV-2 infection but resident remains in care home" category of ordinal outcome.
- Further adjustment for any other covariate not pre-specified in the primary analysis that is predictive of the primary outcome and with marked imbalance between treatment arms at baseline.

7.3. Subgroup analysis of primary outcome

Subgroup analyses will be conducted for the ordinal primary outcome and for all-cause mortality for the following factors for each separate principal comparison:

- Care home type (residential vs mixed nursing/residential vs. nursing)
- Prior COVID-19 in care home at any time (yes vs no)
- Size of Care Home Total number of residents in care home ((small (<30 residents) vs medium (≥30 to <50 residents) vs large (≥50 residents))
- Care home has capacity to give Oxygen (yes vs no)
- age group (<80 vs 80-89 vs ≥ 90 years old)
- sex (female vs male)
- vaccination status (none, partial, full)

The analysis will be conducted by including an interaction term with the allocated treatment in the analysis model (mixed-effects ordinal logistic regression for primary outcome and shared frailty model for all-cause mortality) to assess whether there is evidence that the effects of subgroups differ substantially from the overall effect seen in all patients combined. The models will adjust for the same variables as the primary analysis. Between-group treatment effects will be provided for each subgroup, but interpretation of any subgroup effects will be based on the treatment-subgroup interaction and 95% confidence interval. Results will be presented on forest plots containing the estimated effects with confidence intervals. The descriptive statistics and interaction coefficients and CIs will be presented regardless of the interaction p-values to provide information for any future more targeted trials. The subgroup analyses will be regarded as exploratory as the trial is not powered to detect interactions.

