13.7. Planned Subgroup Analyses

Subgroup analyses will be conducted for the ordinal primary outcome and for all-cause mortality for the following factors for each separate pairwise comparison:

Т	rial	Prophylactic therapy in care homes trial	Protocol	Final v1.0	date:	13-May-2021	Page:	37 of 44
n	name:	U1111-1265-4068	version:					

- (i) type of care home (residential vs residential/nursing vs nursing);
- (ii) previous COVID-19 cases in the care home (yes vs no)
- (iii) care home size: small (≤30 residents) vs medium (>30, ≤50 residents) vs large (>50 residents)
- (iv) Care home has capacity to give oxygen and/or dexamethasone (yes vs no)
- (v) age group (<80 vs 80–89 vs >90 years old)
- (vi) sex (female vs male)
- (vii) vaccination status (none vs partial vs full)

14. Trial Organisational Structure

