2.1. Sample size and justification

A total of 530 residents per group are required to detect an odds ratio of 0.67 for a 4-level ordinal primary outcome (no infection proportion 60%, infection remain in CH 15%, all-cause hospitalisation 10%, all-cause mortality 15%), assuming a two-sided significance level of 5% and 90% statistical power, with no adjustment for clustering [2].

Care homes of varying size will be included, and the number of residents recruited per care home will likely be in the range 20–60. Assuming an intra-cluster correlation of 0.11, a coefficient of variation for care home size of 0.49 (Lothian population analysis in 189 care homes[3]) and an average of 32 residents per care home in the study (assuming that the average number of beds per care home is 40[4] and that not all residents will take part in the study), this gives rise to a design effect or inflation factor of 5.25[5].

Therefore, to compare a single active treatment versus usual care, we will need in the region of 174 care homes, i.e., in excess of 5,500 residents. Allowing for the uncertainty surrounding the parameters listed above (e.g. levels of mortality and transmission rates are expected to be different in the second wave due to improved preparedness, better treatments and the potential impact of the expected vaccination programme, therefore it is possible that the observed proportions in the control group may differ), we propose a sample size of 200 care homes and a total number of residents in the region of 6,400 per comparison, with sample size re-estimation during the trial (once 60-day outcome data are available for at least 75% of residents randomised to standard care).

Therefore, comparing three active (unrelated) treatments concurrently versus standard care (in a 1:1:1:1 allocation ratio) would require 400 care homes in total, corresponding to around 13,000 residents.

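### Effect modification by age is examined only across three age bands; adding a continuous-age interaction would recover about a fifth of the information if the change is roughly linear

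*SAP*

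**What the plan says.** Protocol 13.7 states that "Subgroup analyses will be conducted for the ordinal primary outcome and for all-cause mortality for the following factors for each separate pairwise comparison", and SAP 7.3 repeats the plan. In both, age enters as three bands; in the SAP it is "age group (<80 vs 80-89 vs ≥ 90 years old". The SAP adds a treatment interaction to the mixed-effects ordinal model for the primary outcome and to the shared frailty model for all-cause mortality.

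On reading the results, the SAP says that "interpretation of any subgroup effects will be based on the treatment-subgroup interaction and 95% confidence interval". It then says that interaction coefficients (plural) and their intervals will be shown whatever the p-values, as information for later, more targeted trials. It calls the subgroup analyses exploratory because the trial is not powered for interactions.

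Age is also an entry criterion (65 or over), a listed baseline characteristic (SAP 5.2) and a fixed effect in the primary model (SAP 7.1, which does not say whether it enters as a continuous term). SAP 4.5 expects missing baseline covariates to be very rare. Neither document plans an interaction with age as a continuous variable.

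**The concern.** Individual age is available for almost every resident. Cutting it into three bands treats a resident of 80 and one of 89 as alike, and turns one slope into two interaction coefficients, each relative to a chosen reference band. The SAP bases interpretation on the interaction and its interval, but does not say whether a three-level factor gets a joint test, separate contrasts or a trend score.

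The stake is precision in an analysis meant to inform future trials. Age varies mostly between residents of the same home, so an age interaction should largely escape the design effect of 5.25 that governs the main comparison. It is therefore one of the better-estimated interactions in this trial, and avoidable loss is worth removing.

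**Working it through.** **1. The plan's own figures.** SAP 2.1 states: "A total of 530 residents per group are required to detect an odds ratio of 0.67", "assuming a two-sided significance level of 5% and 90% statistical power". Control proportions are 60%, 15%, 10% and 15%.

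Whitehead's formula is n per group = 6(z₀.₉₇₅ + z₀.₉₀)² / [ln(OR)² × (1 − Σp̄³)].
- At OR 0.67 the active-arm proportions are 0.691, 0.126, 0.077 and 0.106, so 1 − Σp̄³ = 0.7255 and n = 542.
- At OR 2/3, n = 529. Both are close to 530.

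Design effect: 1 + [(0.49² + 1) × 32 − 1] × 0.11 = 5.255. Homes: 2 × 530 × 5.25 / 32 = 173.9, i.e. 174. Planned size: 200 × 32 = 6,400. All of this reproduces.

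**2. Information kept by the bands.** For a linear interaction, this is the between-band share of the age variance, R². The documents give no age distribution for the trial. The background care-home cohort (Protocol 1.2) has a median of 86. I assume normal ages truncated at 65, with mean 82 to 88 and SD 6 to 9.

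| Mean, SD | Share <80 / 80–89 / ≥90 | R² | Loss |
|---|---|---|---|
| 86, 8 | 22% / 47% / 31% | 0.82 | 18% |
| 84, 9 (smallest loss) | 32% / 43% / 25% | 0.83 | 17% |
| 88, 6 (largest loss) | 9% / 54% / 37% | 0.77 | 23% |

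**3. Added cost of a joint test.** At 80% power the non-centrality needed is 7.85 on 1 df and 9.63 on 2 df. With R² = 0.82 the effective loss is 1 − 0.82 × 7.85/9.63 = 33%, or 9.63/(0.82 × 7.85) = 1.5 times the information. Over the whole grid, at 80% or 90% power, the loss is 31% to 38%.

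**4. Power for an assumed interaction.** With 3,200 residents per arm, SE(log OR) = √[6/(3,200 × 0.7255)] = 0.0508. I use this as the SE of the interaction per SD of age, which assumes that clustering largely cancels within homes. An interaction of 0.13 per SD means odds ratios of about 0.59, 0.67 and 0.76 at one SD below the mean, at the mean and one SD above.

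- Continuous age: z = 0.13/0.0508 = 2.56, and power = Φ(2.56 − 1.96), about 72%.
- Bands scored as a trend: z = 2.56 × √R².
- Bands tested jointly: non-central chi-square on 2 df, non-centrality 2.56² × R².

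| Interaction per SD | Continuous | Banded trend, 1 df | Banded joint, 2 df |
|---|---|---|---|
| 0.10 | 50% | 41–43% | 32–34% |
| 0.13 | 72% | 61–64% | 50–54% |
| 0.15 | 84% | 73–76% | 63–67% |

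If clustering left a variance inflation of 1.5, the 0.13 row would fall to 55% for continuous age and 37% for the joint test.

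**5. Simulation.** I took 200 homes of 32 residents with a home random intercept, ages with mean 86 and SD 8 drawn independently of home, and a binary cut of the outcome (3,000 runs). The bands kept 81% of the non-centrality. Where continuous age had 80% power, the banded trend had 73% and the joint test 62%. With no interaction, rejection rates were 4.5% to 5.0%.

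**6. A shape that favours the bands.** Suppose the log odds ratio jumps by 0.4 at age 80 (mean 86, SD 8, so 22.4% are under 80). The non-centrality available is 0.4² × 0.224 × 0.776 / 0.0508² = 10.8, all of it captured by the bands, giving 84% power on 2 df. A straight line in age captures about 52% of it (5.6), giving about 66%.

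**The case against.** The case for leaving the plan alone has four parts, and most of it stands.

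- **Status.** The SAP labels these analyses exploratory and unpowered and reports them whatever the p-value. Power at 5% is therefore only a convenient measure of precision, not a planned criterion. This stands and keeps the point minor.
- **Size.** A reader might infer that banding throws away a third of the information. It does not: banding alone costs about a fifth. A third appears only with a 2-df joint test, which the SAP does not name. Against a trend score on the same bands, the gain from continuous age is roughly 7 to 12 percentage points of power.
- **Shape.** The documents give no reason to expect a linear change. With a step at a cut-point the bands do better, and if only the middle band differed a straight line would have almost no power. This stands, and is why the continuous term should sit alongside the bands.
- **Wording.** A reader might infer that the SAP promises one interaction estimate and cannot deliver it. The same section also plans coefficients in the plural. The test is unspecified rather than contradictory, and care home type, home size and vaccination status, also three-level factors, share the gap.

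A reader might also take the immunosenescence passages in Protocol 1.1 to 1.2.1 as a prediction that the prophylactic effect varies with age. They concern vaccine response and the vulnerability of care home residents as a group, so they do not support that.

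What survives is narrower: age is examined only in bands, and a simple complementary estimate is left out.

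**Conclusion.** The point holds as a low-severity improvement. Under a roughly linear age interaction, the planned bands lose about a fifth of the information, or about a third of effective sample size if a joint 2-df test were used. These sizes rest on an assumed age distribution and interaction size, and on the interaction being estimated mainly within homes. If age differs systematically between homes, absolute power would be lower for every version. The power figures apply to the ordinal outcome; none were computed for all-cause mortality.

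The bands are pre-specified and agree between the two documents, and using them is not an error. The primary analysis, the sample size and the main conclusions are unaffected.

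**What to change.** In SAP 7.3 and Protocol 13.7:

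- Add a treatment by continuous age interaction, per 10 years with a 95% confidence interval, to the mixed-effects ordinal model and the shared frailty model, as the main age-interaction estimate.
- Check non-linearity with a quadratic or spline term and report the result.
- Keep the three bands and their interaction coefficients for the forest plot.
- State how three-level subgroup factors are tested: joint test, contrasts or trend.

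The cost is a few lines of text and one or two extra model terms, with no new data. The downside is that a single estimate assumes an approximately linear change in the log odds ratio (log hazard ratio for mortality) with age. The retained bands and the non-linearity check would show a marked departure.

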7.4. Secondary outcomes

Table 1 lists all the secondary outcomes and the type of variables.

Individual-level secondary outcomes will be analysed using mixed-effects regression models appropriate for the type of outcome variable, adjusting for minimisation variables and individual-level factors including age, sex, and vaccination status as fixed effects with a random effect for care home.

Ordered categorical outcomes will be analysed similarly as the primary outcome.

Continuous outcomes will be analysed using linear mixed-effect model, with further adjustment for baseline outcome measure if available. The estimated between group effect will be presented using the adjusted difference between means, along with a 95% confidence interval.

Binary variables will be analysed using mixed effects logistic regression model. The between group effect will be reported using an adjusted risk difference and adjusted risk ratio along with corresponding 95% confidence intervals, obtained using Stata's Margins command with standard errors computed using the delta method.

All-cause mortality (time to death) will be analysed using mixed-effects Cox regression model (shared frailty model). A Kaplan-Meier curve will be presented by trial arm. Other time-to-event outcomes will be analysed using competing-risks survival regression with cluster–robust standard errors. The between group effect will be reported using an adjusted hazard ratio along with a corresponding 95% confidence interval. Estimated cumulative incidence function graphs will be presented for each of the outcomes by trial arm.

The care home level infection rate outcome will be analysed using multiple linear regression of the cluster proportions, adjusted for the cluster-level minimisation variables, to obtain the adjusted difference in mean rates between the intervention and control arms along with the corresponding 95% CI. Poisson regression on cluster-level rates, adjusted for the cluster-level minimisation variables, will be used to obtain estimated rate ratio with corresponding 95% CI. The regression models will be weighted by the inverse of the variance of each cluster summary to take account of variability in cluster size. For this outcome, there will be no adjustment for individual-level covariates since not all residents will have individual level infection data to allow for individual-level analysis.

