Electronic frailty index at 60 days	Electronic frailty index (eFI) The eFI is presented as a score (e.g. if 9 deficits are present out of a possible total of 36 the FI score = 0.25) - higher scores indicate increasing frailty. The eFI score is used to define frailty categories: - Fit (0 - 0.12) - Mild frailty (> 0.12 - 0.24) - Moderate frailty (> 0.24 - 0.36) - Severe frailty (> 0.36) A composite endpoint strategy will be used to handle the eFI outcome truncated due to death by adding an extra category for death to ensure that death equates to the worst outcome.	-	✓	Ordered categorical	Mixed-effect ordinal logistic regression
Ordinal outcome for the most serious event experienced during the 120 days post- randomisation	Four-level ordinal outcome: No SARS-CoV-2 infection, SARS-CoV-2 infection but resident remains in care home, Admission to hospital, all- cause and Death, all-cause.	✓	✓	Ordered categorical	Mixed-effect ordinal logistic regression
Clinical: care home level					

Page **14** of **25**

Written using WPD 16.5 version 3.0, 13-Sep-2018. Effective date: 13-Oct-2018. Template Author: [name]

Outcome measures	Description	Sourc	es	Type of data	Analysis method
Number of SARS-CoV-2 infections in residents in the care home	Aggregate infection rate in the care home. The numerator will be all confirmed SARS-CoV-2 infections including residents not participating in PROTECT-CH trial and the denominator will be the number of residents in the care home at randomisation.	✓	~	Rate (Proportion)	Linear regression (rate difference) and Poisson regression (rate ratio)
Additional Safety:					
Serious Adverse Reactions (SAR, excluding primary and secondary outcomes) and Suspected Unexpected SAR (SUSAR)		✓			
Adverse events relevant to the intervention as specified in relevant IMP specific appendix to protocol		✓			

*For PEP- only applicable for residents not positive at randomisation; [†]excludes residents with directive for no hospitalisation

Page **15** of **25**

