5.2. Baseline characteristics

Baseline characteristics for cluster and individual participant levels will be summarised both overall and by treatment groups using appropriate descriptive statistics for continuous (mean, standard deviation, median, lower & upper quartiles, minimum, maximum and number of observations) and categorical (frequency counts and percentages) characteristics to illustrate balance between the groups at baseline. Baseline summaries will be based on the principal comparisons (between each treatment group and the concurrent standard care group respectively).

Cluster-level characteristics will include:

- Minimisation variables
 - care home type (residential vs nursing vs nursing and residential dual registration)
 - prior COVID-19 in care home at any time (yes vs no)
 - size of care home Total number of residents in care home (small (<30 residents), medium (>30, <50 residents), large (>50 residents))
 - care home has capacity to give oxygen (yes vs no)
- Any residents in care home received vaccination against COVID-19
- Any staff in care home received vaccination against COVID-19
- Country
- Care home ownership
- Registered for clients with learning disabilities
- CQC rating (outstanding, good, requires improvement) or equivalent in devolved administrations.
- Time between positive test for COVID-19 in resident/member of staff and care home randomisation (For PEP only)

Individual resident level baseline demographic and clinical characteristics will include:

- Age
- Sex
- Ethnicity
- BMI (from height and weight)
- Advance directive for no hospitalisation
- Do Not Attempt Resuscitation order
- Smoking status
- Co-morbidities (diabetes, heart disease, chronic lung disease, severe liver disease, severe kidney impairment, dementia, stroke)
- Previous positive test for COVID-19
- Tested positive for COVID-19 at randomisation (For PEP only)
- Received vaccination for COVID-19
- Time in care home
- Electronic frailty index
- Type of consent

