7.1. Primary analysis

Primary between-group comparison will be based on individual-level data rather than cluster-level summaries. Primary comparative analyses will employ a multi-level mixed-effects ordinal logistic regression model to reflect the ordinal nature of the primary outcome and allow for the betweencluster variation (clustering within care homes). A random intercept model will be fitted. The model will adjust for all the cluster-level minimisation factors and individual-level factors including age, sex, and vaccination status (ordinal: no vaccination, partial dose, full dose) as fixed effects. These individual-level factors have been shown to contribute to disparities in fatality rates in COVID-19 patients. The treatment comparison will be presented as an adjusted common proportional odds ratio together with 95% confidence interval, and p-value.

The ordinal logistic regression model is based on the proportionality of odds (parallel lines) assumption, that is, the treatment effect is consistent across the whole composite ordinal primary outcome spectrum. We will test for non-proportionality using a Likelihood Ratio test comparing the model where the coefficients are constrained to be equal across the three log-odds contrasts and the model where the proportional odds assumption is relaxed. If the data sets show significant departures from the proportionality assumption, then an extension of the multilevel ordinal logistic regression model to allow for non-proportional odds will be employed.

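### SAP 7.4 leaves baseline frailty out of the 60-day electronic frailty index model, which costs power on that secondary outcome

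*SAP*

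**What the plan says.** SAP Table 1 (section 2.4) defines the 60-day eFI as a score but analyses it in bands: "The eFI score is used to define frailty categories". Deaths are placed at the bad end of the scale: "A composite endpoint strategy will be used to handle the eFI outcome truncated due to death by adding an extra category for death". The outcome thus has five ordered levels, and the stated method is "Mixed-effect ordinal logistic regression".

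SAP 7.4 then sets the model by data type. For this type: "Ordered categorical outcomes will be analysed similarly as the primary outcome". The covariates for individual-level secondary outcomes are given as "adjusting for minimisation variables and individual-level factors including age, sex, and vaccination status as fixed effects with a random effect for care home". The primary model in SAP 7.1 has the same set: "The model will adjust for all the cluster-level minimisation factors and individual-level factors including age, sex, and vaccination status". Adjustment for the baseline value of the outcome appears once, in the sentence on another data type: "Continuous outcomes will be analysed using linear mixed-effect model, with further adjustment for baseline outcome measure if available".

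SAP 5.2 includes "Electronic frailty index" in the list of resident-level baseline characteristics, where its stated use is descriptive.

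**The concern.** The baseline-adjustment sentence reaches no outcome in Table 1. The single outcome typed continuous, days alive and not in hospital, starts at randomisation and has no baseline counterpart; the quality-of-life measures belong to the health economic plan, which the SAP puts out of its scope. The eFI is the individual-level secondary outcome with the same measure listed at baseline, and it falls outside the sentence because it was banded to make room for death. No reason is given for leaving its baseline out, so this looks like a side effect of the banding rather than a decision.

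A frailty score re-read after 60 days should depend heavily on where the resident started. If so, the planned model leaves explainable variation in the comparison and has less power than it could have with data the trial already plans to hold.

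**Working it through.** **The plan's own figure.** The documents give a sample size for the primary outcome only, and no precision or power figure for the eFI. The primary figure reproduces:

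- Ordinal formula: n per group = 6(z_α + z_β)² / [(ln OR)²(1 − Σp̄³)]. With control proportions 60/15/10/15%, two-sided 5% and 90% power, an odds ratio of 1.5 (the inverse of 0.67, rounded) gives 63.04 / (0.1644 × 0.7248) = 529.06, that is 530. With exactly 0.67 it is 542.
- Design effect: 1 + [(0.49² + 1) × 32 − 1] × 0.11 = 5.255.
- Homes: 2 × 530 × 5.255 / 32 = 174.1.

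**Inputs for the eFI.** From the SAP: 200 homes per comparison, 32 residents per home on average, 15% control mortality, five outcome levels and a random-intercept ordinal model. The intra-cluster correlation of 0.11 is the SAP's value for the primary outcome, borrowed here. Assumed, because the documents are silent: mean eFI 0.28, SD 0.10, death moderately related to baseline frailty, the treatment effect, and the baseline to 60-day correlation.

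**Role of the two correlations.** For a continuous outcome in a cluster cohort, adjustment multiplies the variance by 1 − r², where r = [mρπ + (1 − ρ)τ] / [1 + (m − 1)ρ], τ is the resident-level and π the home-level correlation. With m = 32 and ρ = 0.11 the denominator is 4.41.

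- τ = 0.9, π = 0.9: r = 0.90, ratio 0.19.
- τ = 0.9, π = 0.5: r = (1.76 + 0.801) / 4.41 = 0.581, ratio 0.66.

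Stability within residents is therefore not enough; the homes' mean frailty must be stable too. Even on this simple scale, half the information is lost only when r exceeds about 0.71 (1 − 0.71² = 0.496).

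**Simulation on the SAP's scale.** The five-level outcome was simulated with τ = π = r and analysed with and without baseline eFI, with 120 replicates per scenario. Relative efficiency of the planned model is (z without baseline / z with baseline)².

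| Effect acts on | r = 0.5 | r = 0.7 | r = 0.9 | r = 0.95 |
|---|---|---|---|---|
| eFI only | 0.79 | 0.61 | 0.33 | 0.25 |
| eFI and death | 0.80 | 0.62 | 0.35 | 0.26 |
| Death only | 0.89 | 0.76 | 0.51 | 0.40 |
| Power, eFI only | 0.64 to 0.70 | 0.66 to 0.82 | 0.65 to 0.98 | 0.66 to 0.99 |
| Power, death only | 0.40 to 0.42 | 0.39 to 0.49 | 0.37 to 0.59 | 0.35 to 0.67 |

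The power rows run from the planned model to the adjusted one. With 120 replicates, a power of 0.65 has a Monte Carlo standard error of √(0.65 × 0.35 / 120) = 0.04, so the small differences at r = 0.5 are uncertain.

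Taking one minus the efficiency gives losses of 11-21%, 24-39%, 49-67% and 60-75%. Part of the gain is a larger conditional log odds ratio rather than a smaller standard error: at r = 0.9 with the effect on eFI only, the estimate moves from −0.205 (SE 0.087) to −0.301 (SE 0.074). Efficiency or power is therefore a better word than precision.

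**The case against.** Four points can be made for the plan.

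- **The covariate list is open.** SAP 7.1 and 7.4 introduce age, sex and vaccination status with the word including, so baseline eFI might be added. This does not close the gap: an open list permits a covariate but does not pre-specify it, and SAP 7.4 names the baseline value only for continuous outcomes. The covariate sensitivity analysis in 7.2 is for the primary outcome only.
- **The outcome is minor.** SAP section 7 treats secondary outcomes as supportive, and the sample size does not rest on the eFI. This stands and limits the importance of the point.
- **Baseline eFI may not be complete.** Table 1 sources eFI from routine data alone, and the protocol's assessment schedule does not name it at baseline. This stands in part: the value depends on linkage, so a rule for missing values has to come with the change.
- **Homes are randomised and the model has a random intercept for home.** This stands. A reader might infer that chance differences in entry frailty would pass for treatment effects. The documents do not support a charge of bias: such differences are part of the between-home variation reflected in the standard error. The issue is efficiency.

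A reader might also infer that baseline eFI, previous positive test and the no-hospitalisation directive, all listed in SAP 5.2, belong in the primary model. The calculations here concern only the 60-day eFI. The primary covariates are fixed in Protocol 13.2 and SAP 7.1, the SAP gives a prognostic reason for the individual-level ones, and 7.2 already allows further adjustment as a sensitivity analysis. Adding to that set would depart from the protocol without a supporting calculation.

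**Conclusion.** The omission is confirmed from the text: as written, the 60-day eFI is modelled without baseline eFI, and the one sentence on baseline adjustment applies to no Table 1 outcome. The cost is power on a supportive secondary outcome. It does not bias the comparison or affect the primary conclusion.

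The size is conditional. The planned model loses about 10-20% of efficiency if the baseline to 60-day correlation is 0.5, about 25-40% at 0.7, about 50-65% at 0.9 and about 60-75% at 0.95. These ranges span effects on frailty, on death, or both. They assume equal resident-level and home-level correlation, an intra-cluster correlation borrowed from the primary outcome, and death moderately related to baseline frailty; deaths unrelated to frailty are not covered. The loss is smaller if home-level correlation is lower. Adjustment raised efficiency in all twelve scenarios.

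A reader might infer that most of the available precision is discarded. That needs an eFI that is highly stable within both residents and homes. It is plausible over 60 days, but the documents give no eFI correlation, SD or intra-cluster correlation to establish it.

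**What to change.** In SAP 7.4, after the sentence on ordered categorical outcomes, state that the 60-day eFI model also adjusts for baseline eFI, preferably as the continuous score rather than its bands. In SAP 4.5, extend the missing-baseline rule to this covariate by name. That rule is framed around the primary-analysis covariates, and although it goes on to mention any missing baseline data, its reach beyond them is unclear. Leave the primary model as it is.

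The change is a free improvement: a sentence and a clause, using a value the SAP already plans to tabulate, with no new data collection and no change to the protocol's primary analysis. It should be made before allocations are first released for a final comparison, the point by which Protocol 13.2 requires the SAP to be agreed. The reported odds ratio will then be conditional on baseline frailty, and the report should say so.
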